12.2 Participant demographics and other baseline characteristics

Demographics, MS disease history, MRI baseline characteristics and MS medication history will be summarized for the FAS.

Relevant medical histories and current medical conditions at baseline will be summarized by system organ class and preferred term.

12.3 Treatments

The duration of exposure in (days) to study medication will be summarized descriptively.

Concomitant medications and significant non-drug therapies prior to and after the start of the study treatment will be listed and summarized according to the Anatomical Therapeutic Chemical (ATC) classification system and preferred term.

12.4 Analysis of the primary endpoint(s)

The primary aim of this study is to explore maintenance of efficacy evaluated by MRI lesions at twelve months after initiating ofatumumab therapy in RMS participants transitioning to ofatumumab from aCD20 therapy (for reasons other than suboptimal response or the occurrence of certain treatment-emergent adverse events).

12.4.1 Definition of primary endpoint(s)

The primary endpoint will be no change or a reduction from Baseline (assessed at Screening Visit) in the number of gadolinium enhancing lesions observed by MRI at Month 12, a binary outcome (yes, no).

12.4.2 Statistical model, hypothesis, and method of analysis

The number and percentage of participants with no change or a reduction in number of gadolinium enhancing lesions at Month 12 will be presented. The 95% confidence interval for the proportion of participants with no change or a reduction will be calculated by using normal approximation method.

Both non-response imputation for missing data and observed data approaches will be applied.

The above analyses will be conducted using the Full-Analysis-Set (FAS).

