4.6 Rationale for Public Health Emergency mitigation procedures

During a Public Health emergency as declared by Local or Regional authorities i.e. pandemic, epidemic or natural disaster, mitigation procedures to ensure participant safety

and trial integrity are listed in relevant sections. Notification of the Public Health emergency should be discussed with Novartis prior to implementation of mitigation procedures, and permitted/approved by Local or Regional Health Authorities and Ethics Committees as appropriate.

5 Population

The study population will consist of adult participants with RMS fulfilling all the eligibility criteria listed below. The study is planned to be conducted in approximately 10-20 centers within the United States. It is aimed to enroll approximately 100 participants. Participants who enroll and prematurely discontinue study will not be replaced.

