12.8 Sample size calculation

12.8.1 Primary endpoint(s)

Sample size calculations were based on the proportion of participants with no change or a reduction from Baseline (assessed at Screening Visit) in the number of gadolinium-enhancing (GdE) MRI lesions 12 months after initiating ofatumumab therapy. Three precision estimates were considered for this study:

The sample size of 100 participants is selected based on budget and early availability of interim analysis results. This sample size of 100 participants will provide us with an 8.5% precision

(half-width of 95% confidence interval), a 7.8% precision, or a 7.0% precision corresponding to estimated proportions of 75%, 80%, and 85% of participants achieving the primary endpoint.

13 Ethical considerations and administrative procedures

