#### **2.1.1.8 Efficacy analysis cut-off**

The efficacy analysis cut-off date is 30.4375 days after the date of last study treatment administration.

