### **2.5.2 Statistical hypothesis, model, and method of analysis**

The primary analysis to address the primary objective will be based on the following estimand:

- Treatment of interest: Following a loading dose regimen consisting of once daily doses on days 1, 7 and 14, ofatumumab is given once monthly starting at Month 1. All doses of ofatumumab will be given subcutaneously via an auto injector at a dose of 20mg.
- Population: Relapsing MS participants currently treated with an infused aCD20 mAb, specifically ocrelizumab or rituximab, that have received at least 2 courses of therapy that are switching due to reasons other than safety or efficacy. Further defined through the appropriate inclusion/exclusion criteria to reflect the target population.
- Variable: Reduction or no change from baseline in the number of GdE lesions as observed by MRI (Yes, No).
- Other intercurrent events: Death or treatment/study discontinuation.
- Summary measure: Proportion of participants with no change or a reduction in the number of GdE T1 lesions at Month 12 and corresponding 95% confidence interval.

The 95% CI for the primary endpoint will be calculated using a normal approximation method. In addition, the change from baseline in the number of GdE T1 lesions will also be summarized descriptively by time point and graphically using a longitudinal plot.

Both non-responder imputation (NRI) for missing data and observed data approaches will be applied.

NRI is a conservative imputation method for dichotomous variables. NRI assumes that a participant is a treatment failure, i.e. non-responder, if they do not have a valid month 12 MRI assessment, or if they discontinue the study prematurely and do not have a valid month 12 MRI assessment. Hence, for missing data the primary variable outcome will be imputed to “No”. MRI assessments occurring after the efficacy cut-off will not be included in the analysis.

The primary analysis of the primary efficacy variable will be based on the FAS.

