### **2.5.4 Sensitivity analyses**

The primary analysis will be repeated to analyze no change or a reduction from baseline in the number of GdE T1 lesions observed by MRI at 12 months of treatment (Yes, No), based on observed data. MRI assessments occurring after the efficacy cut-off will not be included in the analysis.

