#### **2.5.4.1 Supplementary analysis:**

The primary analysis will be repeated to analyze no change or a reduction from baseline in the number of GdE T1 lesions observed by MRI at 12 months of treatment (Yes, No), including any assessments after the efficacy analysis cut-off. Both NRI for missing data and observed data approaches will be applied.

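### The normal-approximation interval fixed for the primary proportion has no rule for results near 100%: it exceeds 100% or has zero width when three or fewer of 80 to 100 participants are non-responders

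*Protocol*

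**What the plan says.** The method is fixed in the protocol summary (data analysis), in Protocol 12.4.2 and in SAP 2.5.2. The protocol wording is "The 95% confidence interval for the proportion of participants with no change or a reduction will be calculated by using normal approximation method", and the SAP wording is "The 95% CI for the primary endpoint will be calculated using a normal approximation method".

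The same interval serves several versions of the primary proportion:

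- SAP 2.5.2: "Both non-responder imputation (NRI) for missing data and observed data approaches will be applied".
- SAP 2.5.4 (sensitivity) repeats the primary analysis "based on observed data. MRI assessments occurring after the efficacy cut-off will not be included in the analysis".
- SAP 2.5.4.1 (supplementary) adds scans after the efficacy cut-off, and again "Both NRI for missing data and observed data approaches will be applied".

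No readable section names another interval, a truncation rule, or a fallback for few or no non-responders. SAP 5.5 adds only that no hypothesis test is planned. Protocol 12.8.1 and SAP 3 justify 100 participants by half-widths of 8.5%, 7.8% and 7.0%, "corresponding to estimated proportions of 75%, 80%, and 85% of participants achieving the primary endpoint".

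**The concern.** The Wald interval behaves poorly when a proportion is close to 100%, and the design makes such a result plausible among participants who are scanned. No change counts as success. Protocol 5.2 excludes people with two or more active Gd+ lesions. Protocol 4.1 describes a population already stable on anti-CD20 therapy, and Protocol 4.5 cites a 4.6% incidence of contrast-enhancing lesions on rituximab. Planning looked only at 75–85%.

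The study has one arm, no comparator and no test, so this interval is the only stated measure of uncertainty for the primary result. Its error favours the claim: the lower limit, which a reader would use to judge whether efficacy was maintained, is too high. An interval above 100% or of zero width would also have to be replaced after the data were seen, which pre-specification is meant to prevent.

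**Working it through.** **Inputs.** From the documents: n = 100 and planning proportions of 75/80/85% (Protocol 12.8.1); 4.6% lesion incidence (Protocol 4.5). Assumed, because the documents give no missing rate: 80 to 100 participants scanned at Month 12, and 0–20% of scans missing. The 4.6% is used as a failure rate (p = 0.954) for illustration only. z = 1.96, z² = 3.8415.

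**1. The plan's own figures.** Wald half-width = z√[p(1−p)/n], n = 100:

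- p = 0.75: 1.96 × √(0.1875/100) = 8.49%
- p = 0.80: 1.96 × √(0.16/100) = 7.84%
- p = 0.85: 1.96 × √(0.1275/100) = 7.00%

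These match 8.5/7.8/7.0%. Wald with continuity correction (8.99/8.34/7.50), Agresti-Coull (8.43/7.85/7.10), Clopper-Pearson (8.89/8.26/7.44) and Wilson (8.38/7.77/6.99) do not match all three, so the method meant is the uncorrected Wald interval.

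**2. Where the upper limit passes 100%.** For p̂ < 1, p̂ + z√[p̂(1−p̂)/n] > 1 when p̂ > n/(n + z²).

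- n = 80: 80/83.84 = 95.4%
- n = 90: 90/93.84 = 95.9%
- n = 100: 100/103.84 = 96.3%

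In whole participants this is one, two or three non-responders at each of n = 80, 85, 90, 95 and 100. At p̂ = 1 the width is zero. At exactly 95% the interval is still in range (95/100 gives 90.7–99.3%).

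**3. Examples.** Wilson limits are [p̂ + z²/2n ± z√(p̂(1−p̂)/n + z²/4n²)] / (1 + z²/n).

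| Responders | Wald (%) | Wilson (%) |
|---|---|---|
| 98/100 | 95.26–100.74 | 93.00–99.45 |
| 88/90 | 94.7–100.8 | 92.3–99.4 |
| 90/90 | 100–100 | 95.9–100 |
| 90/100 | 84.1–95.9 | 82.6–94.5 |
| 85/100 | 78.0–92.0 | 76.7–90.7 |

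**4. Observed data at p = 0.954 (assumed).** The chance of failure is P(X ≤ 3), with X the number of non-responders, Binomial(n, 0.046). Coverage is the exact binomial sum.

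| n scanned | Chance above 100% or zero width | Wald coverage | Wilson coverage |
|---|---|---|---|
| 85 | 45% | 90.1% | 94.0% |
| 90 | 40% | 91.4% | 96.3% |
| 100 | 32% | 94.1% | 95.0% |

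If the true rate were instead anywhere in 0.95–0.99, at n = 100, Wald coverage averages 86% (63–95%) and Wilson 96% (minimum 92.1%).

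**5. Non-responder imputation (NRI), n = 100.** True proportion = (1 − missing) × response among scanned, with response 95.4–100%.

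- 10–20% missing: from 0.80 × 0.954 = 0.76 to 0.90 × 1 = 0.90.
- 5% missing: from 0.95 × 0.954 = 0.91 to 0.95.

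The last two columns give how often the lower limit lies above the true value (nominal 2.5%).

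| Range of p | Mean Wald coverage (range) | Wald lower-limit error (mean) | Wilson lower-limit error (mean) |
|---|---|---|---|
| 0.75–0.85 (planned) | 94.0% | 4.4% | 2.1% |
| 0.76–0.90 | 93.8% (91.1–95.6%) | 4.7% | 2.0% |
| 0.90–0.95 | 92.0% (87.5–95.0%) | 7.2% | 1.4% |

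Averaged on a 0.0005 grid. With 10–20% missing, an upper limit above 100% has a chance below 1%. With three or fewer failures in total, including missing scans, the NRI interval fails too (97/100 gives 93.7–100.3%).

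**The case against.** The strongest reply is that the visible failure sits mainly in the observed-data version, which SAP 2.5.4 classes as a sensitivity analysis. Under NRI every missing Month 12 scan counts as a failure. SAP 2.1.1.8 narrows the usable scans further ("The efficacy analysis cut-off date is 30.4375 days after the date of last study treatment administration"), and Protocol 5 says "Participants who enroll and prematurely discontinue study will not be replaced". These rules pull the proportion away from 100%. At 85/100 and 90/100 the lower limit moves only 1.3 to 1.5 points, and at the planned proportions mean coverage is 94.0%. The objective is exploratory, nothing is tested, and anyone can recompute limits from the reported counts.

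The premise is also indirect. The 4.6% comes from an observational rituximab study, and the protocol does not say whether it is per scan or per patient. The Gd+ exclusion cuts both ways, because a participant with no baseline lesion fails on a single new one. Wilson is not perfect either: over 0.95–0.99 its upper limit falls below the true value 3.9% of the time on average.

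All of this stands and limits the weight of the point. It does not remove it. Protocol 12.4.2 and SAP 2.5.2 commit to the observed-data version, which NRI does not protect. The documents give no missing rate to show that the NRI result is safe. Even at the planned 75–85%, the Wald lower limit errs at 4.4% against a nominal 2.5%.

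**Conclusion.** The concern holds. The specified interval is certain to exceed 100% or collapse to zero width with three or fewer non-responders among 80 to 100 participants, and the plan has no rule for that case. For the observed-data result the chance is 32–45% for 85 to 100 scanned, if the true response is 95.4%. That response rate is an inference; the plan itself assumes 75–85%. For the NRI primary result the effect is modest with 10–20% missing and serious only if about 5% or fewer scans are missing. The lower limit is too high on average throughout. No decision changes, so this should be corrected but does not threaten the study. Confidence is high for the arithmetic and lower for whether the condition will arise.

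**What to change.** Replace the normal approximation with the Wilson score interval for the primary proportion in the NRI, observed-data and supplementary versions at Month 12, and use it for any interval reported at Month 6. Clopper-Pearson limits would also remove the boundary problem, but they are wider (8.9/8.3/7.4% at 75/80/85%). With Wilson, precision at n = 100 is 8.4/7.8/7.0%, so the sample-size statement needs at most a change of 0.1 point at 75%.

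The cost is wording in the protocol summary, Protocol 12.4.2 and SAP 2.5.2, plus a small programming change. If only the SAP is amended, Table 4-1, which now records no changes to the protocol analyses, needs an entry. The change should be made before database lock.

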12.4.3 Handling of intercurrent events of primary estimand

Missing data will be handled using non-response imputation regardless of intercurrent event.

12.4.4 Handling of missing values/censoring/discontinuations

For participants with missing number of gadolinium enhancing lesions at Month 6 and Month 12, non-response imputation method will be used.

12.4.5 Sensitivity and Supportive analyses

Neither sensitivity nor supportive analysis is planned.

12.5 Analysis of secondary endpoints

12.5.1 Efficacy endpoint(s)

Retention on ofatumumab treatment from baseline to Month 6, and to Month 12 (yes, no) will be summarized using frequency count and percentage for the FAS.

12.5.2 Safety endpoints

For all safety analyses, the safety set will be used. All listings and tables will be presented by treatment. Unless explicitly otherwise stated, only data up to and until B cells are repleted after the final study drug administration for study completers or until the participant initiates a commercial MS disease modifying therapy or until the end of Safety Follow-up for premature withdrawals will be included in the analysis and data beyond this time point for a participant will be excluded from safety analysis. In addition, a separate summary for death including on treatment and post treatment deaths will be provided. In particular, summary tables for adverse events (AEs) will summarize only on-treatment events, which started or worsened during the on-treatment period (treatment-emergent AEs).

The on-treatment period for safety analysis lasts from the date of first administration of study drug until B cells are repleted after the date of the last actual administration of study drug for study completers or until the participant initiates a commercial MS disease modifying therapy or until the end of Safety Follow-up.

Adverse events

All information obtained on adverse events will be displayed by treatment and participant. The number and percentage of participants with AEs of special interest/related to identified and potential risks will be summarized in the following ways:

[figure not shown]
- By treatment, primary system organ class and preferred term.
- By treatment, primary system organ class, preferred term and maximum severity.
- By treatment, pre-defined topic of interest, primary system organ class and preferred term.

Separate summaries will be provided for study medication related adverse events, serious adverse events, and other significant adverse events leading to discontinuation.

The number and percentage of participants with adverse events of special interest will be summarized by treatment, primary system organ class and preferred term. A participant with multiple AEs within a category is only counted once towards the total of that category.

Vital signs

All vital signs data may be listed by participant, and visit. Abnormalities will be flagged. Descriptive statistics for change from baseline will be provided by visit.

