### **2.8.1 Adverse events (AEs)**

An adverse event (AE) is any untoward medical occurrence (i.e., any unfavorable and unintended sign [including abnormal laboratory findings], symptom or disease) in a participant or clinical investigation of a participant after providing written informed consent for participation in the study. That means that a participant can report AEs before having started study medication. For reporting purposes, the main focus will be on treatment emergent adverse event (TEAE), defined as any adverse event which started on or after the day of first dose of study drug, or before 30 days after treatment end date, if severity at baseline if missing or if post baseline severity is greater than baseline severity.

The number (and percentage) of participants with TEAEs will be summarized in the following ways:

- by primary SOC and PT
- by primary SOC, PT and maximum severity

Separate summaries will be provided for:

- study drug related TEAEs
- serious adverse events (SAEs)
- TEAEs leading to permanent study drug discontinuation
- TEAEs leading to study drug interruption

The MedDRA version used for reporting the study will be described in a footnote. Missing CTCAE grades will not be imputed. If a participant reported more than one AE with the same PT, the AE with the greatest severity will be presented. A participant with multiple AEs within a primary SOC is only counted once towards the total of the primary SOC.

All AEs will be listed.

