### **2.8.1.1 Adverse events of special interest / grouping of AEs**

Selected AEs will be considered under the heading of adverse events of special interest (AESI) and described in the electronic Case Retrieval Sheet (eCRS). The eCRS that is current at the time of the database lock will be used and AESIs will be identified where the flag Core safety topic risk (SP) = 'Y'. The search criteria for the AESI will be included in the TFL shell document.

AESI will be summarized by category and preferred term for the SAF, and will also be listed.

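### SAP 2.8.1.1 omits the AESI severity and SOC summaries listed in protocol 12.5.2 and gives the AESI table no first-dose start, while SAP Table 4-1 declares no change (minor)

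*Protocol*

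**What the plan says.** **Protocol 12.5.2.** The list of AE tables opens with this sentence: "The number and percentage of participants with AEs of special interest/related to identified and potential risks will be summarized in the following ways". Three layouts follow: by SOC and preferred term; "By treatment, primary system organ class, preferred term and maximum severity"; and by pre-defined topic, SOC and preferred term. A later sentence in the same section returns to AESIs without severity: "The number and percentage of participants with adverse events of special interest will be summarized by treatment, primary system organ class and preferred term". The section also states that "summary tables for adverse events (AEs) will summarize only on-treatment events, which started or worsened during the on-treatment period", and it fixes the start of that period: "The on-treatment period for safety analysis lasts from the date of first administration of study drug until B cells are repleted".

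**SAP 2.8.1.1.** AESIs are drawn from AEs in general: "Selected AEs will be considered under the heading of adverse events of special interest (AESI". One table and a listing are planned: "AESI will be summarized by category and preferred term for the SAF, and will also be listed".

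**SAP 2.8 and 2.8.1.** All safety analyses are limited to data before the safety cut-off, which is an end limit only. Section 2.8.1 gives TEAEs as the main focus of reporting and plans a TEAE table by SOC, preferred term and maximum severity. It also points out that AEs can precede dosing: "That means that a participant can report AEs before having started study medication".

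**SAP Table 4-1.** No change to the protocol-specified analyses is declared.

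**The concern.** There are two gaps between the documents, and the change table mentions neither.

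First, a severity summary that the protocol lists for AESIs has no counterpart in the SAP's AESI section, and the SOC level has gone as well.

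Second, the protocol starts AE tables at the first dose, whereas the SAP's AESI section states no start. AEs are collected from informed consent (protocol 10.1.1). Screening lasts up to 28 days and falls within 4 to 9 months of an infusion of another anti-CD20 antibody (protocol 5.1). In a single-arm study no control group shows the background rate. An infection or similar event from screening, if it reached the AESI table, would be read as an event on ofatumumab. TEAEs are a secondary endpoint, so the boundary of these tables should be explicit.

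**Working it through.** The point rests on no stated figure, so the check is a side-by-side reading.

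**Content of the AESI tables**

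| Layout in protocol 12.5.2 | Counterpart in SAP 2.8.1.1 |
|---|---|
| SOC, preferred term | None for AESIs |
| SOC, preferred term, maximum severity | None for AESIs; SAP 2.8.1 has this layout for all TEAEs |
| Topic, SOC, preferred term | Approximated by category and preferred term, without SOC |

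Of three listed layouts, the SAP keeps an approximation of one. SAP section 1 says that the SAP describes the methods of protocol section 12 and any deviations from them. An entry in Table 4-1 was therefore due.

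**What the general severity table recovers.** For an AESI identified by a single preferred term, the preferred-term row in the TEAE severity table gives the same counts by grade. Two things cannot be read there: SOC totals restricted to AESIs, and a participant's worst grade across several preferred terms within one AESI category. The first belongs to the protocol's layout. The second does not, because the protocol's severity item is by SOC and preferred term and its topic item carries no severity.

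**Start boundary**

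1. Protocol 12.5.2: only on-treatment events, from first administration.
2. SAP 2.8: an end limit only.
3. SAP 2.8.1: TEAEs are the main focus, which does not restrict every table. The SOC and preferred-term, severity, drug-related, discontinuation and interruption tables are each labelled TEAE.
4. SAP 2.8.1.1: AEs, with no such label.

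No SAP sentence tells a programmer to remove a pre-dose AESI from this table.

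**Whether the TEAE label alone would repair it.** The TEAE definition in SAP 2.8.1 joins its two time conditions with *or*: onset on or after the first dose, or before 30 days after the end of treatment. Read literally, an event during screening meets the second condition. The severity clause that follows does not clearly remove it. The label therefore sets a start only once the conjunction is corrected.

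**Size.** The most screening time that could be counted is 100 × 28/365.25 = 7.67 person-years, if all 100 participants used the full 28 days. Turning that into events needs a pre-dose AESI rate. The documents give none, so no expected count is offered.

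**The case against.** The strongest reply is that the SAP already carries the protocol's intention. Its TEAE table by SOC, preferred term and maximum severity has the layout of the protocol's severity item. If the protocol's opening sentence is taken literally, section 12.5.2 has no general SOC and preferred-term table for AEs at all, although TEAEs are a secondary endpoint. The sentence may simply be badly worded, and the SAP may have applied the first two layouts to all TEAEs as meant. The protocol's second AESI sentence, without severity, fits that reading. On the start boundary, 2.8.1.1 is a subsection of 2.8.1, whose focus is TEAEs. The SAP claims to follow protocol section 12. Its labelling is also not strict, since the SAE summary in 2.8.1 carries no TEAE label either. The table shells, which were not available, may settle the matter.

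Much of this stands, and it rules out two stronger readings that a reader might infer:

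- *The trial could not report how severe the class risks were.* The documents do not support this. Grades by preferred term are tabulated for TEAEs, and all AEs and AESIs are listed. Protocol 4.5 cites 99% of systemic injection reactions as Grade 1-2, but as background from earlier trials; no comparison with it is planned.
- *Pre-dose AESIs will be counted as ofatumumab events.* The SAP is silent; it does not say so. Reactions to ofatumumab injections cannot occur before the first dose, and acute infusion reactions to the previous drug are implausible 4 to 9 months later. Infections remain possible.

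The reply does not remove the mismatch itself. The protocol's list names AESIs, the SAP's AESI section omits severity and SOC, and the SAP refers to the shells only for the AESI search criteria. An intention that has to be inferred is not a specification.

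**Conclusion.** The mismatch holds, at minor priority. The SAP plans no AESI-specific severity table and no SOC level for AESIs, it does not expressly exclude AESIs that began before the first dose, and Table 4-1 records none of this. The loss is limited to summaries specific to AESIs; severity by individual preferred term survives elsewhere. The number of pre-dose AESIs is unknown and may be zero.

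This conclusion assumes that the protocol's opening sentence means what it says about AESIs and that the unseen shells add no restriction. The remark on worst grade across a category matters only if a category pools several preferred terms, which the documents do not show. The protocol's two AESI statements differ on severity and also need reconciling.

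A separate difference is not resolved here: the protocol's on-treatment period runs to B-cell repletion, start of a commercial MS therapy or the end of Safety Follow-up, while the SAP's safety cut-off falls about 30 days after treatment ends.

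**What to change.** 1. **SAP 2.8.1.1.** State that treatment-emergent AESIs are tabulated (a) by category and preferred term and (b) by category, preferred term and maximum CTCAE grade, with each participant counted once, at the worst grade. The category-level grade is a small addition to the protocol's SOC and preferred-term layout, so note in Table 4-1 that category replaces SOC.
2. **SAP 2.8.1.** Join the time conditions of the TEAE definition with *and*: onset or worsening on or after the first dose, and no later than the safety cut-off. Without this, step 1 does not set a start.
3. **Alternative to the severity table.** If AESI severity is to stay out, list the dropped AESI severity and SOC summaries in Table 4-1 as changes from protocol 12.5.2. The first-dose start should still be stated.

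The cost is a few lines of SAP text and one further table from the existing AE dataset. No new data are needed.
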